###### Safety (throughout the entire Period):

- Occurrence of all adverse events with particular emphasis on thromboembolic events (TEEs) and hemolytic transfusion reactions (HTRs).
- Local injection site reactions.
- Vital signs (blood pressure, heart rate, body temperature and respiratory rate).
- Physical examination.
- Laboratory parameters (hematology, clinical chemistry, urinalysis).

###### Safety:

- Tests for viral safety (at Baseline and end of Treatment Period).
- Pregnancy test, if applicable (at Screening and end of Treatment Period) .

#### 3.2 Overall Study Design and Plan

This study is planned to start in Q3 2018 and to be completed by Q2 2020, resulting in an overall duration of 24 months.

It will be a double-blind, randomized, placebo-controlled, parallel group, multicenter, comparative efficacy and safety study in a minimum of 78 adult subjects of both genders with

[figure not shown]
definite or probable DM according to the criteria of Bohan and Peter [29, 30] who have previously responded to IGIV therapy.

As DM is a rare disease, about 45 sites are projected to participate in countries worldwide with emphasis on European countries and North America.

Subjects eligible after screening will be randomized 1:1 to receiving up to 32 infusion cycles of either *octanorm* 0.5 g/kg/week or placebo every week for 32 weeks. The weekly infusion will be performed in two separate sessions (= 1 infusion cycle for a given weekly administration). An infusion cycle comprises both sessions to be administered on 1 or 2 days, either on the same day or on two consecutive days or with maximum one day in between two sessions.

In case of clinically important deterioration (for definition see Section 4.3.1) during the SC treatment period, subjects will be discontinued from the study, will undergo a termination visit and may optionally receive Octagam 10% as IGIV rescue medication (2g/kg BW one time, provided by the sponsor) or rescue treatment according to standard of care at the site by the treating physician. Octagam 10% or any other commercially available IGIV as optional IGIV rescue medication can be also reimbursed by the sponsor (2g/kg BW one time). IGIV as rescue medication should be administered with infusion rate not higher than 0.04 mL/kg/min (240 mg/kg/h).

**Figure 1: Scheme of Study Design**

### 3.3 Discussion of Study Design and Choice of Control Group(s)

#### 3.3.1 Study Design

The study design includes all major scientific, state-of-the-art interventions needed to assess the efficacy, safety and tolerability of therapeutic treatments in DM patients.

*octanorm* or placebo (see below) will be administered subcutaneously every week ( $\pm 2$  days) using a syringe driver for precise infusion rates. The total dose/volume of a weekly infusion will be calculated on the basis of the body weight. The weekly infusion will be performed in two separate sessions (= 1 infusion cycle for a given weekly administration). An infusion cycle comprises both sessions to be administered on 1 or 2 days, either on the same day or on two consecutive days or with maximum one day in between two sessions.

During the first four weeks (first 4 infusion cycles), all infusions will be administered at the study site. Apart from Visit 3, where at least the first session of an infusion cycle will also be administered at the site, the next two weeks can be performed either at the patient's home by the mobile healthcare research nurses or at the site (decision to be taken by Investigator and patient based on previous experience). Thereafter, SCIG infusions will be administered at home by mobile healthcare research nurses, apart from Visits 4-9, where at least the first session of an infusion cycle will be administered at the site. Before starting home treatment, a diary will be provided to the patients for documenting AEs and local tissue reactions at injection sites, body temperature around 1 hour after the end of the infusion, and any changes in concomitant drug and non-drug therapies between visits. The date of home treatments, batch numbers, number of vials, volume and speed of infusion, number and location of injection sites will be recorded by the mobile nurses. Based on the Investigator's decision a home infusion can be replaced with an on-site infusion if considered medically relevant.

In case of clinically important deterioration during the SC treatment period, subjects will be discontinued from the study, will undergo a termination visit, and may optionally receive Octagam 10% as IGIV rescue medication (2g/kg BW one time, provided by the sponsor) or rescue treatment according to standard of care at the site by the treating physician. Octagam 10% or any other commercially available IGIV as optional IGIV rescue medication can be also reimbursed by the sponsor (2g/kg BW one time). IGIV as rescue medication should be administered with infusion rate not higher than 0.04 mL/kg/min (240 mg/kg/h).

### **3.3.2 Control Group(s)**

The efficacy and safety of weekly SCIG infusions in DM have not been studied in well-controlled and adequately powered randomized clinical trials.

Therefore, *octanorm* will be compared with placebo in this trial.

### **3.3.3 Study Parameters**

The study parameters selected in the study are appropriate to verify the clinical efficacy of SCIG in DM.

Patients with "clinically important deterioration" as defined in Section 3.1.1 will be classified as non-responders. The proportion of non-responders will be used as primary endpoint. Clinically important deterioration was defined by the study Steering Committee, consisting of several experts in the field, based on available clinical data and experience. The definition combines established measures of muscle weakness/skin involvement (MMT-8/CDASI) with physician's disease activity assessment. The definition of Oddis et al. 2013 [31] used in other studies including ProDERM was considered too sensitive for well-maintained patients with low disease activity at study entry, and had thus to be adapted.

The CDASI is a clinician-scored single page instrument that separately measures activity and damage in the skin of DM patients for use in clinical practice or clinical/therapeutic studies. The modified CDASI (version 2) is the one in current use. The modified CDASI has 3 activity measures (erythema, scale, and erosion/ulceration) and 2 damage measures (poikiloderma and calcinosis) which are assessed over 15 body areas. In addition, Gottron's papules on the hands are evaluated both for activity and damage. Lastly, the activity of periungual changes and alopecia is assessed.[32]

Core Set Measures of myositis disease activity have been established and validated by the IMACS Group for DM/PM clinical trials.[33-36] Very recently, the CSM have been further developed into conjoint-analysis hybrid response criteria combining 6 CSM to determine clinically meaningful improvement in a Total Improvement Score (TIS).[37]

Property of Octapharma. Do not copy or distribute without written permission.

## 4 STUDY POPULATION

### 4.1 Population Base

In total, 78 adult male or female subjects with DM who have responded to treatment with intravenous immunoglobulin, and have been on a stable dose of 2g/kg BW (+/- 10%) for at least 3 months will be enrolled into the study.

#### 4.1.1 Inclusion Criteria

Subjects who meet all of the following criteria are eligible for the study:

1. Subjects with diagnosis of definite or probable DM according to the Bohan and Peter criteria.[29, 30]
2. Subjects who have responded to IGIV treatment as assessed by the treating physician and being on a stable dose for at least 3 months on 2g/kg bodyweight (+/- 10%) prior to study enrolment.
3. For subjects being on other medication(s) for the treatment of DM (immunosuppressants, corticosteroids): a) subject was on such medication(s) at the start of IGIV treatment in the first place, and b) received such medication(s) for at least 3 months prior to study enrolment and at a stable dose for at least 4 weeks prior to study enrolment at the maximally allowed conditions as per Table 2 (see section 4.2.1).
4. MMT-8 score  $\geq 144$ , with at least 3 other CSM to be normal or near normal as per the following criteria: Visual Analogue Scale [VAS] of patient global disease activity  $\leq 2$  cm, physician's global disease activity  $\leq 2$  cm, extra-muscular disease activity  $\leq 2$  cm; no muscle enzyme  $>4$  times upper limit of normal due to myositis, Health Assessment Questionnaire [HAQ]  $\leq 0.25$ .
5. Males or females  $\geq 18$  to  $<80$  years of age.
6. Voluntarily given, fully informed written consent obtained from subject before any study-related procedures are conducted.
7. Subject must be capable and willing to understand and comply with the relevant aspects of the study protocol.

#### 4.1.2 Exclusion Criteria

Subjects who meet any of the following criteria are *not* eligible for the study:

1. Cancer-associated myositis, defined as the diagnosis of myositis within 2 years of the diagnosis of cancer (except basal or squamous cell skin cancer or carcinoma in situ of the cervix that has been excised and cured - at least 1 year for basal or squamous cell skin cancer and 5 years for carcinoma in situ of the cervix must have passed since excision).
2. Evidence of active malignant disease or malignancies diagnosed within the previous 5 years (including hematological malignancies and solid tumors) or breast cancer diagnosed within the previous 10 years. Subjects  $>5$  years ( $>10$  years for breast cancer) of cancer diagnosis who have been treated and are in remission are allowed.
3. Subjects with overlap myositis (except for overlap with Sjögren's syndrome), connective tissue disease associated DM, inclusion body myositis, polymyositis, juvenile dermatomyositis or drug-induced myopathy.

4. Subjects with immune-mediated necrotizing myopathy with absence of typical DM rash.
5. Subjects with generalized, severe musculoskeletal conditions other than DM that prevent a sufficient assessment of the subject by the physician.
6. Subjects who received blood or plasma-derived products (other than IGIV) or plasma exchange within the last 3 months before enrolment.
7. Subjects with administration of permitted concomitant medications exceeding the maximally allowed conditions as per section 4.2.1.
8. Subjects with administration of forbidden concomitant medications within the washout periods as defined in Table 3: see section 4.2.2.
9. Subjects starting or planning to start a physical therapy-directed exercise regimen during the trial. Subjects on stable physical therapy for >4 weeks are allowed but the regimen should remain the same throughout the trial.
10. Cardiac insufficiency (New York Heart Association III/IV), cardiomyopathy, significant cardiac dysrhythmia requiring treatment, unstable or advanced ischemic heart disease.
11. Severe liver disease, with signs of ascites and hepatic encephalopathy.
12. Severe kidney disease (as defined by estimated glomerular filtration rate (eGFR) < 30 mL/min/1.73 m^2).
13. Known active or chronic hepatitis B, hepatitis C or HIV infection. Past hepatitis B or C infection that has been cured is allowed.
14. Subjects with a history of deep vein thrombosis within the last year prior to study enrolment or pulmonary embolism ever.
15. Body mass index > 40 kg/m^2 and/or body weight > 120 kg.
16. Medical conditions whose symptoms and effects could alter protein catabolism and/or IgG utilization (e.g. protein-losing enteropathies, nephrotic syndrome).
17. Known IgA deficiency with antibodies to IgA.
18. History of hypersensitivity, anaphylaxis or severe systemic response to immunoglobulin, blood or plasma derived products or any component of *octanorm* 16.5% such as polysorbate 80 or to sodium chloride.
19. Known blood hyperviscosity, or other hypercoagulable states.
20. Subjects with a history of drug abuse within the past 5 years prior to study enrolment.
21. Participating in another interventional clinical study with investigational treatment within 3 months prior to study enrolment. Subjects who participated in the Octagam 10% Dermatomyositis Study (GAM10-08) can be included.
22. Women who are breast feeding, pregnant, or planning to become pregnant, or are unwilling to apply an effective birth control method (as per protocol section 7.3.9 b) up to four weeks after the last IMP infusion received.

## 4.2 Prior and Concomitant Therapy

The following must be recorded in the electronic case report form (eCRF):

- Details of any DM-related medications received within 12 months before screening.
- Details of any other medications received within 3 months before screening.
- Concomitant medications throughout the study.

- Non-drug therapies incl. physiotherapies within 4 months before screening and throughout the study.

#### 4.2.1 Permitted Concomitant Therapy

Previous medications for the treatment of DM (immunosuppressants, corticosteroids) must either be

- a) washed-out, i.e. patients can be included into this study only when the following washout periods prior to randomization are considered:
  - 3 months for leflunomide, topical application of Tacrolimus;
  - 8 weeks for methotrexate, azathioprine, cyclosporine, tacrolimus, mycophenolate mofetil, acthar, hydroxychloroquine, corticosteroids.

or

- b) continued if subject received medication at the start of IGIV treatment in the first place and for at least 3 months prior to study enrolment and at a stable dose for at least 4 weeks prior to study enrolment (details see Table 2); however, only one concomitant therapy in addition to corticosteroids is allowed. Topical application of Tacrolimus is allowed in addition to one immunosuppressive drug.

Table 2 specifies which DM-related medications are permitted as concomitant therapy. Only 1 concomitant therapy in addition to corticosteroids is allowed. In addition, the maximal allowed dose which has to remain stable throughout the study is provided.

Throughout the entire treatment period, the dose regimen of concomitant therapies should not be changed to avoid interference with the efficacy endpoint evaluation. However, when safety reasons intervene, concomitant therapies may be changed by the investigator in the interest of the patient.

The routine use of premedication for Ig administrations to alleviate potential side effects is not allowed during the study. However, if a subject experiences 2 consecutive infusion-related AEs that are likely to be prevented by premedication, antipyretics, antihistamines, or antiemetic drugs are allowed before the following infusions of study drug. The dose of premedication should be held stable during the study (except when safety reasons intervene) and its use must be documented.

Local anesthetics to reduce pain associated with needle insertion are allowed.

NSAIDs or opioids are commonly used in DM patients and are therefore allowed. The dose of such medications should be kept stable 2 weeks prior to study enrolment and during the study (except when safety reasons intervene). The use of such medication must be documented.

Topical medication, except topical steroids, is allowed. Such topical medication should be kept stable during the study to avoid interference with the extra-muscular activity, one of the CSM.

However, topical steroids for moderate or severe local injection site reaction treatment are allowed. When possible ultra high potency (very potent) topical steroids should be used with recommended twice-daily treatment duration 3 days, maximum 7 days. The purpose and assignment regimen of treatment should be documented.

The mobile research nurses are not permitted to make any therapy assignments on their own, including premedication; any therapy changes are always to be Investigator's decisions.

Physical therapy-directed exercise regimen is allowed if started  $\geq 4$  weeks prior to study enrolment and kept on a stable schedule, frequency and extent. Any such exercise regimen must be documented.

**Table 2: Dose Limitations for Prior/Concomitant DM-Related Medications**

Only *one* concomitant therapy in addition to corticosteroids is allowed!\*

Drug	Maximally allowed stable dose as concomitant therapy
Immunosuppressive Drugs	
Methotrexate	25 mg/week
Azathioprine	2 mg/kg
Cyclosporine	2 mg/kg
Tacrolimus	0.2 mg/kg
Mycophenolate mofetil	3000 mg daily
Leflunomide	20 mg daily
Acthar	80 IU twice a week
Other	
Hydroxychloroquine	400 mg daily
Corticosteroids	10 mg daily prednisone equivalent

\*Note: Topical application of Tacrolimus is allowed in addition to one immunosuppressive drug.

#### 4.2.2 Forbidden Concomitant Therapy

The following medications or therapies are forbidden during participation in this study:

- Routine premedication to alleviate potential tolerability problems, with the exception of permitted therapy as stated above.
- Corticosteroids at any dose if given as premedication to alleviate potential side effects.
- Drugs in Table 2 at doses higher than stated.
- Other blood or plasma-derived products should only be given for emergency reasons.
- Plasma exchange procedures.
- Live attenuated vaccines such as measles, rubella, mumps and varicella.
- Any experimental drug.

Table 3 lists further medications that are forbidden, but patients can be included into this study when the respective washout period is considered.

**Table 3: Forbidden Concomitant Medications**

Drug	Washout Period
Monoclonal antibodies (e.g. adalimumab, infliximab, certolizumab, golimumab, abatacept, tocilizumab)	8 weeks
Rituximab	12 months or 6 months plus normal CD19 count
Cyclophosphamide	3 months
Etanercept	4 weeks
Anakinra	2 weeks
Rilanocept	8 weeks
Topical steroids (except for local injection site reaction treatment)	2 weeks

#### 4.2.3 Rescue Medication

Octagam 10% as optional rescue medication for patients with clinically important deterioration during the treatment period will be provided by the sponsor according to local regulation. Octagam 10% or any other commercially available IGIV as optional IGIV rescue medication can be also reimbursed by the sponsor (2g/kg BW one time). IGIV as rescue medication should be administered with infusion rate not higher than 0.04 mL/kg/min (240 mg/kg/h). The use of Octagam 10% or any other IGIV as rescue medication will be recorded.

### 4.3 Withdrawal and Replacement of Subjects/Patients

#### 4.3.1 Premature Subject/Patient Withdrawal

Subjects have the right to withdraw from the study at any time for any reason, without the need to justify their decision. The Investigator also has the right to withdraw subjects in case of AEs, poor compliance, or other reasons. Since an excessive rate of withdrawals can render the study non-interpretable, any unnecessary withdrawal by investigator's decision should be avoided.

For any withdrawals after study entry, the Investigator will obtain all the required details and document the reason(s) for discontinuation. If the reason for withdrawal of a subject/patient is an AE, the main specific event or laboratory test will be recorded, and the Investigator will make thorough efforts to clearly document the outcome.

Should a subject decide to withdraw, the Investigator will make the best efforts to complete and report the observations. The Investigator will document the reason(s) for withdrawal of each subject in the eCRF.

Subjects who terminate the study prematurely are drop-outs. The Investigator has to organize the Drop-out visit which is identical to the Termination visit procedures.

Other reasons for premature termination of subjects may be:

1. Withdrawal of subject's consent.
2. Deterioration of DM.
3. Pregnant subjects will be immediately excluded from the study.
4. Investigator's opinion that the subject may be severely harmed if he/she continues trial participation, namely by the treatment and procedures according to the study protocol.
5. Occurrence of a disease which interferes with the study treatment or represents an exclusion criterion.
6. Administration of IgG other than *octanorm*.

"Clinically important deterioration" is defined as follows:

- 1) MMT-8 worsening  $\geq 6$  points (scale of 150) OR CDASI (Total Activity Score) worsening  $\geq 5$  points,  
AND
- 2) Physician's Global Disease Activity VAS worsening  $\geq 2$  cm.

In case of clinically important deterioration during the treatment period, subjects will be discontinued from the study, will undergo a termination visit and may optionally receive Octagam 10% as IGIV rescue medication (2g/kg BW one time, provided by the sponsor) or rescue treatment according to standard of care at the site by the treating physician. Octagam 10% or any other commercially available IGIV as optional IGIV rescue medication can be also reimbursed by the sponsor (2g/kg BW one time). IGIV as rescue medication should be administered with infusion rate not higher than 0.04 mL/kg/min (240 mg/kg/h).

#### **4.3.2 Subject/Patient Replacement Policy**

Patients withdrawn from the study because of safety or efficacy reasons will not be replaced; these premature terminations will in any case establish deteriorations and be analyzed as such. Patients withdrawn from the study for any other reason, e.g. major protocol violation, pregnancy or administrative reasons will also not be replaced. However, if there is a substantial number of withdrawals, the Sponsor and the Coordinating Investigator will consult with the IDMC (without breaking the blind), and decide on a possible replacement policy.

#### **4.4 Assignment of Subjects/Patients to Treatment Groups**

The registration of subjects as screened/randomized will be managed via an interactive response technology (IRT) system.

The screening ID will be a 5-digit number with the first digit being the study number ("2"), the next 2 digits identifying the center (01, 02, ...) and the last 2 digits the sequence number assigned by the IRT (01, 02, ...) for each site continuously. Leading zeros will be used for center and subject numbers below 10. The second subject screened at center 4 will be identified as e.g. 20402.

The Investigator will enter the screening ID into the confidential subject identification list.

If the subject qualifies, randomization will be done centrally through the IRT. The fact that a subject has been randomized will be reported immediately and automatically by the system to

the Investigator, the contract research organization (CRO) and the sponsor. The result of randomization, i.e. the treatment group assignment, will however only be accessible to study personnel not involved in the conduct or analysis of the trial. The unblinded hospital pharmacist or designee will be informed through the system about the vials to be dispensed for a patient. The responsible monitor(s) will be informed of new subjects enrolled automatically by the IRT system via email.

The subject will be identified by the previously assigned screening ID throughout the trial. Under no circumstances are subjects who enroll in the study permitted to re-enroll.

#### **4.5 Relevant Protocol Deviations**

Deviations from the protocol should be avoided. A complete list of all minor and major deviations will be compiled and provided for preparation of the clinical study report.

Examples of relevant protocol deviations that will be addressed are:

- Subjects who entered the study even though they did not satisfy the entry criteria.
- Subjects who developed withdrawal criteria during the study (see Section 4.3.1).
- Subjects who received the wrong treatment or incorrect dose (also see Section 5.4).
- Subjects who received an excluded concomitant treatment or a change in the permitted DM-related therapies.
- Subjects who had no CSM or CDASI at Week 32 or Drop-Out Visit.

In case of any major protocol deviation, the Investigator and Octapharma will decide on the further participation of the subject/patient in this study after having discussed all relevant aspects.

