#### **6.2.3.2 Early Termination at an Individual Study Centre**

At any time, the study can be terminated at an individual centre if:

- The centre cannot comply with the requirements of the protocol.
- The centre cannot comply with GCP standards.
- The centre's first patient is not recruited by 20 weeks after initiation of the centre.
- The required recruitment rate is not met.

Should the study be prematurely terminated, all study materials (IMPs, etc.) must be returned to the Sponsor.

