### 9.1 Determination of Sample Size

The sample size calculation is based on the target parameter for the evaluation of the primary endpoint, i.e. the proportions of patients with clinically important deterioration in the active treatment arm (*octanorm*, 0.5 g/kg/week) and the Placebo arm until the end of the 32 week treatment period.

Patients who drop out prematurely or receive rescue treatment for any safety reason or lack of efficacy will also be analysed as patients with clinically important deterioration.

The following assumptions for the true proportion of patients to be analysed as patients with clinically important deterioration, which will include all dropouts, were chosen for the sample size calculation after thorough discussion with Steering Committee members involved in the treatment of DM patients:

- Octanorm arm: 27% (this corresponds to a failure rate of 18.89% in patients randomised to octanorm who completed the study per protocol plus a 10% drop-out rate)
- Placebo arm: 58% (this corresponds to a failure rate of 53.33% in patients randomised to Placebo who completed the study per protocol plus a 10% drop-out rate)

The pair of hypotheses to be tested is:  $H_0: P_O = P_P$  vs.  $H_A: P_O \neq P_P$

where  $P_O$  and  $P_P$  denote the proportions of patients with clinically important deterioration in the *octanorm* and Placebo arm respectively.

With these assumptions, a sample size of 39 patients per treatment arm will be needed to achieve a power of 80% to detect a difference between the group proportions, using the Pearson Chi-square Test for Proportion Difference at a significance level of  $\alpha=0.05$ . It is therefore planned to enrol a minimum of 78 patients, randomized to the two treatments groups in a balanced 1:1 ratio.

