### 9.2 Statistical Test Procedure

To test the null hypothesis  $H_0$  against the alternative hypothesis  $H_A$  a two-sided Pearson Chi-square Test for Proportion Difference will be performed at a significance level of 5% to compare the placebo group against the high dose group.

If a subject is prematurely withdrawn from the study, or misses data required for the evaluation of the primary endpoint, this subject will be analysed as a treatment failure, i.e. as having a clinically important deterioration.

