10.1. Primary Endpoint

The primary endpoint measure 'clinically important deterioration' is medically defined in section 8.4, and will be assessed throughout the study until the last visit at Week 32. For the analysis of the primary endpoint, a patient will be considered to have a clinically important deterioration

- (i) if the subject fulfills the definition given in section 8.4 at any time during the treatment period
OR
- (ii) if the subject was withdrawn from the study or received rescue treatment for any reason

If a subject is prematurely withdrawn from the study prior to week 32, or misses data required for the evaluation of the primary endpoint, this subject will be analyzed as a treatment failure, i.e. as having a clinically important deterioration. Because of the double-blind design of the study, and because there is no conceivable connection between the randomized treatment arm and events completely unrelated to study procedure (like e.g. relocation to another city or pregnancy), we trust that any such cases will be distributed uniformly between the treatment arms, and thus not distort the statistical evaluation.

However, to verify this assumption, each withdrawal will be assessed individually by an independent team of medical experts, in compliance with an EU Member State request, and the primary efficacy endpoint will also be analyzed on basis of their individual evaluation of treatment stops. This committee will assess for each patient individually whether she/he should be analyzed as failure or non-failure, based on the reason for treatment stop as well as all other relevant data available. The patients affected by this procedure will be listed with a brief statement justifying the individual classification. This analysis will be done for the FAS and the PP population, and any differences to the primary endpoint outcome will be discussed in the report.

The proportions of patients with clinically important deterioration within the *octanorm* and the placebo arm will be compared by means of the Pearson Chi-square Test for Proportion Difference as implemented in the SAS FREQ-procedure, when specifying the /chisq option for a 2x2 table statement. A confidence level of $\alpha=0.05$ will be applied, and the associated 95% confidence limits for the proportion (risk) difference will be presented.

The pair of hypotheses tested is: $H_0: P_O = P_P$ vs. $H_A: P_O \neq P_P$

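### A joint sponsor–investigator decision to end participation after a protocol deviation, or a withdrawal for administrative reasons, turns a stable patient into a primary-endpoint deterioration

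*Protocol*

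**What the plan says.** Protocol 4.5 lists examples of relevant deviations, among them an incorrect dose and a change in permitted dermatomyositis therapy. It then states: "In case of any major protocol deviation, the Investigator and Octapharma will decide on the further participation of the subject/patient in this study". It gives no criterion for that decision.

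Protocol 4.3.2 treats such removals as an expected category: "Patients withdrawn from the study for any other reason, e.g. major protocol violation, pregnancy or administrative reasons will also not be replaced".

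SAP 10.1(ii) counts a patient as deteriorated "if the subject was withdrawn from the study or received rescue treatment for any reason". Protocol 9.2 and 9.7.1 and SAP 8.2 and 8.3 also count premature withdrawal as a failure.

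One limit on withdrawals is stated, in Protocol 4.3.1, and it concerns the investigator: "Since an excessive rate of withdrawals can render the study non-interpretable, any unnecessary withdrawal by investigator's decision should be avoided".

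The wording of the scoring rule is not uniform. Protocol 9.1 first ties it to safety or lack of efficacy, then says the assumed rates include all dropouts. Protocol 4.3.2 says that safety and efficacy withdrawals are scored as deteriorations, but says of the other withdrawals only that they are not replaced. SAP 6, 8.2 and 10.1 apply the rule whatever the reason.

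**The concern.** The primary endpoint is meant to record loss of disease control. Under these provisions, part of it can record a decision about study conduct. A patient with stable MMT-8, CDASI and Physician's Global scores who receives an incorrect dose may be taken out by agreement between sponsor and investigator. That patient then counts exactly as one whose disease flared.

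These events differ from the ones the plan uses to justify its rule. Protocol 9.7.1 and SAP 10.1 argue from events wholly unrelated to study procedure, such as relocation or pregnancy. A decision taken after a dosing deviation arises from study procedure, and where the patient is willing to keep attending visits it is avoidable. The plan also already has a place for such deviations: Protocol 9.5 and SAP 7 remove significant deviators from the per-protocol (PP) set and keep the FAS for the primary analysis.

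At stake are power and the clarity of the estimate. The sample size has almost no reserve above 80%.

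**Working it through.** **1. Inputs.**
- Test, Protocol 9.2: "a two-sided Pearson Chi-square Test for Proportion Difference will be performed at a significance level of 5" per cent.
- Size, Protocol 9.1: "a sample size of 39 patients per treatment arm will be needed to achieve a power of 80" per cent, and it is "planned to enrol a minimum of 78 patients, randomized to the two treatments groups in a balanced 1:1 ratio".
- Event rates, Protocol 9.1: 58% on placebo and 27% on octanorm, with a 10% drop-out rate counted as events in each arm.

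**2. Rates.** Composite = 0.10 + 0.90 × completer failure rate.
- Placebo: 0.10 + 0.90 × 0.5333 = 0.580.
- Octanorm: 0.10 + 0.90 × 0.1889 = 0.270.

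Both agree with the plan. The drop-out allowance is 0.10 × 39 = 3.9, about 4 patients per arm.

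**3. Sample size.** With p̄ = (0.58 + 0.27)/2 = 0.425,

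n = [1.960·√(2 × 0.425 × 0.575) + 0.842·√(0.58 × 0.42 + 0.27 × 0.73)]² / 0.31² = (1.370 + 0.559)² / 0.0961 = 38.7, so 39 per arm.

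The plan's figure reproduces. Normal-approximation power at 39 per arm is 80.3%. Summing exact binomial probabilities over all 2×2 tables in which the Pearson statistic reaches the 5% critical value gives 80.9%.

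**4. Extra removals.** Suppose m patients per arm, beyond the 10%, are removed for reasons unrelated to their disease and scored as failures. Some would have failed anyway, so the expected rate is p′ = p + (m/39)(1 − p), and the difference shrinks by the factor 1 − m/39. For m = 2: placebo 0.58 + (2/39) × 0.42 = 0.602; octanorm 0.27 + (2/39) × 0.73 = 0.307; difference 0.294.

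| Extra removals per arm (assumed) | Placebo | Octanorm | Difference | Exact power |
|---|---|---|---|---|
| 0 | 58.0% | 27.0% | 31.0 points | 80.9% |
| 1 | 59.1% | 28.9% | 30.2 | 78.6% |
| 2 | 60.2% | 30.7% | 29.4 | 76.2% |
| 3 | 61.2% | 32.6% | 28.6 | 73.8% |
| 4 | 62.3% | 34.5% | 27.8 | 71.3% |

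**5. Type I error.** With the same underlying failure rate (53.33%) in both arms and equal removal of 10%, 20% or 30%, the exact rejection rate stays between 5.1% and 5.2%. Inflation needs unequal removal: 10% on octanorm against 20% on placebo gives 7.1%.

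**6. Unequal removal in the other direction.** If the extra removals fell on octanorm only, 2 would bring power to 69.7% and 4 to 56.6%. The documents give no basis for expecting either pattern.

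**The case against.** The case for leaving the text alone is substantial.

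- *The rule is disclosed and deliberate.* Protocol 9.7.1 calls it conservative and explains it, and the assumed rates already carry 10% drop-outs as events. This stands. The loss in the table needs removals beyond that allowance, and their number is an assumption.
- *Independent experts will re-classify each withdrawal*, in the FAS and the PP set, with a justification per patient. Drop-out visits include the core set measures and CDASI, so the experts will normally know the status at exit. This stands as a useful sensitivity analysis. It does not change the primary result, and it cannot show what later visits would have found.
- *Withdrawals may be replaced.* Protocol 4.3.2 provides for a blinded consultation with the data monitoring committee and a possible replacement policy if withdrawals become substantial, and 78 is a minimum. This could restore some power, but would not remove the unrelated events.

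Four stronger readings are tempting, and the documents do not support them.

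- *The sponsor can remove patients on its own.* Under 4.5 the decision is joint, follows discussion, covers continuing as well as stopping, and is taken under the blind.
- *Every removal is scored.* The FAS holds only patients who satisfy all major eligibility criteria (Protocol 9.5, SAP 7), so a patient removed for a major eligibility failure is outside it.
- *All such removals are needless.* Some may be made for safety, and the point does not reach those.
- *Closing a slow-recruiting centre makes its patients events.* Protocol 6.2.3.2 does not say they are withdrawn. Its closing sentence, "Should the study be prematurely terminated, all study materials (IMPs, etc.) must be returned to the Sponsor", does not say so either, and 6.2.3 requires consideration of patients' interests when the study ends as a whole or at a centre. About 45 sites for 78 patients is 78/45 = 1.7 per site, which is the planned average and no evidence that closures with patients on treatment are likely. What is left is an unstated detail.

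**Conclusion.** The point holds in a limited form. Read together, Protocol 4.5 and 4.3.2 and SAP 10.1(ii) allow a stable FAS patient to become a primary event through a decision unrelated to disease. One such removal per arm beyond the 10% allowance is enough to take exact power from 80.9% to 78.6%; four per arm take it to 71.3% and the expected difference from 31.0 to 27.8 points. These figures rest on the plan's own rates, on removals independent of outcome and equal between arms, and on assumed counts.

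A reader might infer a risk of a false-positive result. Equal removals under a kept blind do not produce one: they dilute the effect and work against the product. The reason to act is that the loss is avoidable at little cost.

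**What to change.** 1. In Protocol 4.5 and 4.3.2, state that a major protocol deviation or an administrative reason alone does not end study follow-up. The patient stays in the already scheduled MMT-8, CDASI and Physician's Global VAS assessments to Week 32, is analysed in the FAS on the observed outcome, and has the deviation handled through the PP set. Decisions on study treatment and rescue stay as the protocol has them.
2. Keep the failure rule for patients who actually leave the study, and keep the expert re-classification as a sensitivity analysis.
3. Reconcile the narrower scoring wording in Protocol 9.1 with the unrestricted wording in SAP 6, 8.2 and 10.1, so that one rule applies.
4. As a clarification only, say in Protocol 6.2.3.2 what happens to the follow-up of patients already randomised at a centre closed for slow recruitment.

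The cost is a short protocol amendment with a matching SAP edit, and a few deviating patients completing visits that are already planned. The sample size need not change.
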